This study will enroll approximately 250 patients with schizophrenia and 50 demographically (age/gender) matched control subjects. Depending on the success of our methods, the overall study is projected to last up to 5 years. An individual subject's participation will generally consist of six visits (a screening/questionnaire/interview visit, three stimulation visits with fMRI or EEG and two non-stimulation visits with fMRI or EEG).

In addition to a clinical/screening visit, this study will incorporate a crossover design consisting of 5-10 sessions separated by at least 24-48 hours.

For these sessions, the tDCS protocol (sham with task, DLPFC with task, sham without task, DLPFC without task, or SMC stimulation) may be followed by fMRI or EEG. Up to 4 tDCS sessions (2 sham, 2 stim) may be conducted without fMRI or EEG afterwards. The order of sessions (sham with task, DLPFC with task, sham without task, DLPFC without task, or SMC stimulation) will be randomized and counterbalanced for each group (patients and controls).

The estimated study completion date is March 1, 2022, with all subjects expected to be enrolled by March 1, 2021, and all primary analyses complete by March 1, 2022.

6) Study Endpoints

Participation for each subject is considered complete following participation in all of the tDCS conditions and sessions (sham with task, DLPFC with task, sham without task, DLPFC without task, and SMC stimulation) for an experiment. Although we do not anticipate any safety concerns, studies may be terminated prior to completion in the case of any skin irritations, lesions or other adverse reactions to stimulation. Subjects may also choose to withdraw at any point during the study.

7) Procedures Involved

Recruitment Methods. Healthy young adult participants will be recruited by ads and word of mouth from the UC Davis community; ads will be placed in the Department of Psychology, Center for Neuroscience, or UCDMC as well as around the community (grocery stores, churches, community centers, coffee shops, etc). These flyers are included in the IRB application. Ads will also be placed on our lab web page. Additional subjects will be recruited through the Sona system paid

PROTOCOL TITLE: The Effects of Transcranial Direct Current Stimulation on the Neuronal Mechanisms of Cognitive Control in Schizophrenia

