what you see on screen or generating your own verbal responses, or picking from among a group of answers on the screen.

The participant will also fill out a standard MRI screening questionnaire he or she can be safely included in the study. If the researcher is using electronic consent forms, the subject will be asked to use the mouse or sign pad to place their electronic signature, and we will email an electronic copy of the signed consent. Then, they will be explained all of the experimental procedures by the experimenter. Because it is not clear whether tDCS has any reliable effects on CC or brain activity, we may adjust tDCS stimulation parameters during the study. More specifically, tDCS may vary with the type of current (direct current or sham stimulation), magnitude of current (up to 2 mA), time of stimulation (up to 20 minute) and stimulation sites. The difference between sham and direct current stimulation is that sham stimulation only persists for the first minute of stimulation (after which it is removed) whereas direct current stimulation will last up to 20 minute. Only sites designated by the Starstim cap will be used. The Starstim cap only has standard electrode sites from the 10-20 system. Note that, although different stimulation parameters may be utilized, these differences will not affect the safety or tolerability of the procedure.

Subjects will undergo sham and direct current stimulation on separate visits separated by at least 24-48 hours. Subjects will be blinded to their condition on each visit. During the first visit, we will inform the subjects the number of visits and all the stimulation conditions they will be doing for the specific experiments. However, they will not know which visit is for which condition (the active tDCS or sham conditions) and we will give the same instructions for every visit. The order of the active versus sham conditions will be fully counterbalanced across subjects. Many participants can feel the onset of the stimulation (which leads to a brief tingling or itching sensation), but people cannot generally feel the continued stimulation beyond one minute. By beginning the active and sham stimulation conditions with a period of stimulation, we can ensure that participants will not know if they are receiving either type of active or sham stimulation.

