We will use tDCS to stimulate specifically the DLPFC or SMC, and we will concurrently measure the effects of the stimulation on CC by means of behavioral measurements of accuracy and reaction time. These may be combined with fMRI or EEG after some of the stimulation sessions to measure brain response during a CC task as well as the resting state. The fMRI and EEG measurements are noninvasive. The CC paradigm we will use is described below.

Prior to the start of an experiment, the experimenter will explain all of the experimental procedures to the participants, and the participants will read and sign consent forms if they agree to participate. To familiarize subjects with test procedures, prior to tDCS stimulation subjects will complete a short practice session on the DPX task on a computer screen outside of the MRI scanner. Subjects unfamiliar with MRI scanning procedures may also participate in a mock scanning session (mock scanner that visually resembles the actual MRI scanner) prior to tDCS.

For fMRI sessions, subjects will perform the DPX and RISE tasks while lying supine in the MRI scanner. For EEG sessions, subjects will be seated in a

PROTOCOL TITLE: The Effects of Transcranial Direct Current Stimulation on the Neuronal Mechanisms of Cognitive Control in Schizophrenia

comfortable chair in front of a computer screen. Participants will be presented with visual (e.g., a picture of an object) stimuli. Participants will be asked to make responses to the series of visual stimuli using a numbered pad or keyboard. To constrain learning strategies, participants may be asked to make a simple perceptual or semantic judgment about each stimulus. See below for further details regarding the DPX and RISE tasks. At the end of the session, participants will be debriefed and they will remain in the laboratory in a relaxed state until mood and mental state return to baseline. More details about the experimental design are highlighted below.

Following the completion of each experiment, participants will be fully debriefed on the goals and hypotheses of the experiment and be given the opportunity to provide feedback regarding their experiences and strategies that they used in the study. Below is a table summarizing the possible stimulation parameters that may be used in the proposed experiments:

Stimulation sites	Number of stimulation electrodes	Stimulation electrodes	Current parameters

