In the three-back task, subjects will be asked to remember the location of an object presented three objects previously on a computer screen. To register a match, a key on a keypad, keyboard, or mouse will be pressed. No response is required for non-targets.

Wash up: The stimulating electrodes will be removed, cleaned, and disinfected according to the manufacturers instructions. As the electrodes are removed, the experimenter will inspect the skin at and near the electrode sites for redness, irritation, or damage and note if present.

For sessions that include fMRI scans, scanning will begin immediately following wash-up and will last up to 1 hour (Stimulation will only last for 20 minutes). See above for specific imaging procedures.

Mood Assessment (30-90 minutes):

PROTOCOL TITLE: The Effects of Transcranial Direct Current Stimulation on the Neuronal Mechanisms of Cognitive Control in Schizophrenia

After imaging is complete, participants will undergo a relaxation period (~30 minutes) during which the electrodes will be removed and the participants will relax (by sitting quietly or watching a video). Subjects will then take the mood and mental state questionnaire again to make sure that they have no lingering effects of the stimulation. In the unlikely case that a subject still has any lingering effects, the subject will relax for an additional 15 minutes, and then repeat the mood/mental state assessment. This will be repeated until the participant returns to baseline. There are no known reports of lingering effects of tDCS after 90 minutes, so we anticipate that the relaxation period will be complete within 90 minutes in all participants. We will also perform a 48-hour follow-up call or email to ensure that subjects have not experienced any additional adverse effects.

Compensation. Subjects will be compensated \$25 for completing the questionnaires and clinical interview, \$25 for each tDCS session that does not include fMRI or EEG afterwards, \$75 for each tDCS session that is followed by fMRI or EEG, and given a \$50 bonus for completing all sessions of a given modality (EEG or fMRI).

8) Data and/or Specimen Management and Confidentiality

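### The full debrief on hypotheses is timed to the end of each experiment, so a participant who goes on to a second five-visit set could hear them with up to 5 of 10 masked sessions still to come

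*Protocol*

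**What the plan says.** The relevant text is in sections 5, 6 and 7 of the protocol.

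- **End-of-session debrief** (section 7, account of the fMRI and EEG sessions): "At the end of the session, participants will be debriefed and they will remain in the laboratory in a relaxed state". The sentence goes on to the return of mood and mental state to baseline. It does not say what the debrief contains.
- **Hypothesis debrief** (section 7, shortly afterwards): "Following the completion of each experiment, participants will be fully debriefed on the goals and hypotheses of the experiment". Participants are also invited to comment on the strategies they used.
- **Masking** (section 7, General Procedure): "Subjects will be blinded to their condition on each visit". At the first visit, "we will inform the subjects the number of visits and all the stimulation conditions they will be doing for the specific experiments". The text continues: "However, they will not know which visit is for which condition".
- **Number of sessions** (section 5): "this study will incorporate a crossover design consisting of 5-10 sessions separated by at least 24-48 hours".
- **Size of an experiment** (section 7, tDCS stimulation): five tDCS visits. Section 6 treats participation as complete once all conditions and sessions for an experiment have been done.
- **Modalities** (section 7, Compensation): a bonus is paid for "completing all sessions of a given modality (EEG or fMRI").

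**The concern.** The trial compares conditions within the same person, so the comparison relies on participants approaching every session with the same expectations. The protocol ties full disclosure of the hypotheses to the end of an experiment, not to the end of the participant's masked sessions. For anyone whose sessions extend beyond one experiment, those are different moments.

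The hypotheses have a direction. Section 2 expects DLPFC stimulation to improve DPX performance, and the section 7 text on the no-task sessions and the concurrent n-back task suggests that performing a task during stimulation may add benefit. The behavioural measures are accuracy and reaction time, which a participant's expectations may influence. The contrast most exposed is task versus no task, because a participant always knows whether a task was performed. Sham masking gives no protection there.

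Counterbalancing the order of conditions does not remove the problem. It balances a shift in performance that affects all conditions alike. It does not balance a shift that differs by condition, and that is the kind a known directional hypothesis could produce.

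**Working it through.** The protocol gives no figure of its own on this point. The check sets the provisions side by side and counts the masked sessions left after the hypothesis debrief.

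**Inputs**
- Visits in one experiment: 5 (section 7, tDCS stimulation).
- Sessions per participant: 5 to 10 (section 5).
- Timing of the hypothesis debrief: after completion of each experiment (section 7).
- Completion of an experiment: all its conditions and sessions done (section 6).
- Two five-visit sets per participant: an assumption, not stated outright.

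**Step 1: one set.** Masked sessions remaining = 5 − 5 = 0. The debrief follows the last masked session and does no harm.

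**Step 2: two sets.** Masked sessions remaining after the first set = 10 − 5 = 5. Share of all sessions = 5/10 = 50%.

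**Step 3: is the two-set assumption reasonable?** The upper limit of 10 equals 2 × 5, and a bonus paid per modality fits a participant who does one set with EEG and another with fMRI. The other source of extra sessions in section 5 is the allowance of up to 4 tDCS sessions without imaging. If these are added to one set, the total is 5 + 4 = 9, which does not reach 10. Two sets is therefore the natural reading of a 10-session course, but it remains an inference. Section 5 also says that participation generally consists of six visits, one of them for screening, which corresponds to a single set of five.

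**Step 4: what the participant would know.** From the first visit: the number of visits and the list of conditions. After the hypothesis debrief: also which conditions are expected to do better. Still withheld: which visit carries which condition. Known at every visit without being told: whether a task is performed.

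**Result.** Between 0 (one set) and 5 (two sets) masked sessions could follow the hypothesis debrief. The protocol does not say how many participants would do a second set, so the number affected, and the size of any bias, cannot be derived.

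**The case against.** The strongest case on the other side is that the hypothesis debrief is already placed correctly. Section 6 makes completion depend on all conditions and sessions of the experiment, and the invitation to comment on strategies used in the study reads like an end-of-participation conversation. No text says that a participant repeats the five conditions in a second modality. This stands for one-set participants, probably the usual case given the six-visit description, and it is why the finding is conditional.

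Three stronger readings are tempting, and the documents do not support them.

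- **That the end-of-session debrief gives away the hypotheses, so that every session after the first is affected.** The protocol names goals and hypotheses only in the later, full debrief. The end-of-session sentence concerns wellbeing, and the Mood Assessment text in section 7 describes relaxation, a repeat questionnaire and a follow-up contact, with no mention of purpose. What can fairly be said is that nothing limits its content.
- **That an experiment means a single visit.** Section 12 does use the word loosely in that way when describing the sensation and mood questionnaires. Sections 6 and 7 use it for the whole set of conditions where they deal with completion and visit numbers, and that is the sense that bears on this debrief.
- **That participants are unblinded.** No text discloses allocation, and section 7 expressly keeps the link between visit and condition masked. Knowing a hypothesis does not tell a participant which session was sham.

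It is also fair to object that the main cognitive control measure is the difference between AY and BX performance, and nothing shows that general effort would move it. That is accepted: the direction and size of any effect are unknown.

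**Conclusion.** The point holds in a limited form. The timing rule allows full disclosure of directional hypotheses between two sets of masked sessions. For a participant with two five-visit sets, up to 5 of 10 sessions (50%) could follow that disclosure; for a participant with one set, none would.

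This rests on two assumptions: that an experiment is the five-visit set, as sections 6 and 7 indicate, and that some participants do a second set, which the 10-session limit and the per-modality bonus suggest but do not state. The consequence is an expectancy risk, greatest for task versus no task. It is not a failure of masking. The end-of-session debrief is a gap in wording only. The change is worth making because it removes an avoidable source of bias at almost no cost.

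**What to change.** Amend section 7 in two places.

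1. State that information on goals, hypotheses and condition order is withheld until the participant's last masked session across all experiments and modalities.
2. State that the end-of-session debrief covers only mood, sensations and safety.

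It would also help to define an experiment once and say whether a participant may do a second five-visit set.

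The cost is a few sentences. Participants still receive the full debrief, only later, and the conditions, assessments and sample size are unchanged.

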“Stimulation Only” or “Stimulation and EEG” electrodes may be used (see electrode chart above). Note, for ease of these experiments, the “Stimulation Only” electrodes will be used in most cases. For these electrodes, sponge electrodes will be moistened (with saline), prior to placement on the subject’s scalp. Alternatively, “Stimulation and EEG” electrodes (PISTIM) will be applied using conductive electrode gel. See chart above for electrode sizes and specification. Up to 8 electrodes may be used at any given time (in addition to external/reference electrodes. See above). Only scalp electrode sites designated on the Starstim cap will be used. The cap only uses standard electrode sites from the 10-20 system.

tDCS stimulation (~25 minutes). During this phase, participants will first receive a few minutes of training on the DPX task and complete a brief practice session. Subjects will also be familiarized with the working memory task (see below). After practice, stimulation (or sham stimulation) will begin.

Following the practice session, subjects will undergo sham with task, DLPFC with task, sham without task, DLPFC without task, or SMC active stimulation. The order of the conditions will be fully counterbalanced across subjects. This experiment involves five tDCS visits, and may include tDCS at any of the designated scalp electrode sites in the Starstim cap. Each stimulation visit will be separated by at least 24-48 hours.

Subjects will receive up to 20 minutes of tDCS stimulation or sham, in addition to a few seconds of ramp up and ramp down time at the beginning and end of each session, using the Starstim device. All subjects will receive up to 2.0 mA for the first 30-60 s of stimulation. Current strength will be ramped down, and then reduced to 0.0-0.1 mA in subjects receiving sham stimulation for the remainder of the session. The active stimulation subjects will continue to receive up to 2.0 mA stimulation. Many participants can feel the onset of the stimulation (which leads to a brief tingling or itching sensation), but people cannot generally feel the continued stimulation beyond one minute. By beginning both the active and sham stimulation conditions with a period of stimulation, we can ensure that participants will not

PROTOCOL TITLE: The Effects of Transcranial Direct Current Stimulation on the Neuronal Mechanisms of Cognitive Control in Schizophrenia

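### Does the undefined promise of full counterbalancing of five conditions, with only 50 controls, require a change to the plan?

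*Protocol*

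**What the plan says.** Three sentences of the protocol bear on the order of conditions.

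- Section 7, tDCS stimulation, lists five conditions (two sham, three active) and states: "The order of the conditions will be fully counterbalanced across subjects". It adds: "This experiment involves five tDCS visits".
- Section 7, General Procedure, in the paragraph on blinding of subjects: "The order of the active versus sham conditions will be fully counterbalanced across subjects".
- Section 5, Study Timelines, says that the order of sessions "will be randomized and counterbalanced for each group (patients and controls").

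Section 5 gives the sizes: "This study will enroll approximately 250 patients with schizophrenia and 50 demographically (age/gender) matched control subjects". It describes the schedule in two ways: "this study will incorporate a crossover design consisting of 5-10 sessions separated by at least 24-48 hours", and, for a typical subject, "three stimulation visits with fMRI or EEG and two non-stimulation visits with fMRI or EEG" after a screening visit.

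On persistence, section 3 says that effects of tDCS outlast the stimulation itself. Section 7, Mood Assessment, says: "There are no known reports of lingering effects of tDCS after 90 minutes".

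The protocol gives no number of sequences, no block size and no definition of full counterbalancing.

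**The concern.** In a within-subject comparison over five visits, the order list is the main protection against practice effects (visit position) and carry-over (preceding condition). It is fixed before the first subject is treated and cannot be repaired in the analysis. Full counterbalancing, taken literally, means that every possible order is used equally often. Five conditions have 120 orders and there are 50 controls, so the promise seems impossible in that group.

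The three sentences also name different targets: the order of all conditions across subjects, the order of active versus sham across subjects, and randomised counterbalancing within each group. These are not equivalent. A list could balance position perfectly and still place each condition always after the same predecessor. If carry-over then had to be modelled, precision could fall sharply.

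**Working it through.** **Inputs.** Five conditions, two sham and three active, in five visits (section 7, tDCS stimulation); about 250 patients and 50 controls (section 5). The protocol states no figure of its own on this point, so there is none to reproduce. The calculation assumes one visit per condition, equal and independent errors within a subject, and, where carry-over is fitted, an additive effect of the preceding visit only.

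**1. Which readings can be met?**

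| Reading | Controls (50) | Patients (250) |
|---|---|---|
| All 5! = 120 orders equally often | 50/120 = 0.42: impossible | 250 = 2 × 120 + 10: each order twice, 10 left over |
| Each condition equally often in each of 5 positions | 50/5 = 10 | 250/5 = 50 |
| Each of the 5 × 4 = 20 ordered neighbour pairs equally often (4 per subject) | 50 × 4/20 = 10 | 250 × 4/20 = 50 |
| Each of the 5!/(3! 2!) = 10 active/sham patterns equally often | 50/10 = 5 | 250/10 = 25 |

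The last three can be met together. With A, B the two shams and C, D, E the three active conditions, the ten orders ABECD, ACDEB, BDCAE, BEADC, CABDE, CEDBA, DAEBC, DBCEA, ECBAD, EDACB put every condition in every position twice, use each neighbour pair twice and use each active/sham pattern once. Groups of 50 and 250 are whole multiples of ten. Only the all-orders reading fails outright in the controls.

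**2. What does imperfect balance cost?** The measure is the variance of a difference between two conditions, in units of σ²/n, with subject and period fitted (σ² is the error variance of one visit, n the group size).

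- *Position balanced, no carry-over in the model:* each condition is seen n times, so the variance is 2.000.
- *Position and predecessor balanced, carry-over fitted.* On contrasts, the information per subject is 1 for direct effects and 4/5 − 1/25 = 19/25 for carry-over effects. The cross term has size 1/5, because each ordered pair occurs n/5 times. Adjusted information is 1 − (1/5)²/(19/25) = 18/19, so the variance is 2 × 19/18 = 2.111.
- *Five cyclic orders only.* Each condition has a single predecessor, so five pairs occur 4n/5 times and the other fifteen never. Adjusted information is 1 − (4/5)²/(19/25) = 3/19, so the variance is 2 × 19/3 = 12.67. Without carry-over in the model it is again 2.00.

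Simulated random lists, for comparison:

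| List | Variance, carry-over fitted | Relative to 2.111 | Standard error ratio |
|---|---|---|---|
| Controls: 50 different orders out of 120 | 2.165 (5th–95th percentile 2.14–2.19) | 1.026 | √1.026 = 1.013 |
| Controls: 50 independent random orders | 2.205 | 1.045 | 1.022 |
| Patients: every order twice plus 10 | 2.112 | 1.000 | 1.000 |
| Patients: 250 independent random orders | 2.129 | 1.009 | 1.004 |

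Without carry-over, the control figures are 2.024 (50 different orders) and 2.042 (independent orders) against 2.000, standard error ratios of 1.006 and 1.010.

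**3. Missed visits.** If 10% of visits are missed at random (an assumption), balanced blocks give 2.49 and 50 different random orders 2.56. At 20% the figures are 3.01 and 3.08. The gap stays at 2–3% of variance.

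**4. Do the sentences conflict?** The word for full balance is attached to subjects as a whole. The sentence that speaks of each group promises only randomisation and counterbalancing. Pooled, 300/120 = 2.5, so every order can occur at least twice. The active/sham sentence restricts nothing said elsewhere, and a list balanced over all conditions can satisfy it. The impossibility appears only when the strongest word of one sentence is joined to the smallest group of another.

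**The case for a change.** The best case for a change is that the order list is irreversible, that the wording admits a poor list, and that a better sentence is cheap. A cyclic list could be called counterbalanced, yet it costs six-fold in variance (12.67/2.111 = 6.0) if carry-over is fitted and uses at most 5 of the 10 active/sham patterns. Carry-over cannot be excluded from this document: the 90-minute statement concerns recovery of mood and mental state, and no figure is given at the 24–48 hour gap. A standard Williams block of ten also covers only 5 of the 10 patterns, so a strict reading of the active/sham sentence would not be met by default.

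The arithmetic stands, and so does the observation that the term is undefined. The inference to harm does not. The cyclic list is an invented example, section 5 says the order is randomised, and even that list loses nothing unless carry-over is modelled. Effects that outlast stimulation and an absence of known effects after 90 minutes are compatible statements, with visits at least a day apart. The strict ten-pattern reading is one of several; under a looser one, balancing active and sham by position and precedence, the Williams block suffices.

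A prescribed block would also need more than one new sentence. The ten orders would have to be randomised within each block, the split between fMRI and EEG would have to be handled, and the first two visits would reveal the remaining order to anyone holding the list.

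**Conclusion.** The concern is a gap in wording that whoever prepares the randomisation list fills sensibly; no change to the plan follows. Exact equal use of all 120 orders is unattainable in 50 controls, but the protocol does not clearly promise it there, and every form of balance that matters for the comparison can be had in both groups. Against a perfectly balanced list, a randomised list of different orders costs controls about 1.3% in standard error with carry-over fitted and about 0.6% without. In patients the variance loss is nil to 1%. Details of sequence lists and block sizes commonly belong in a randomisation or analysis plan, which is not at hand.

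This rests on one visit per condition, first-order carry-over at most, and a list that is in fact randomised and counterbalanced by group, as section 5 says. The mismatch between 5–10 sessions in section 5 and five tDCS visits in section 7 is a separate point. It should be reconciled for its own sake, and any sequence list depends on it, but it does not make the counterbalancing sentence an error.
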